## 11 SAFETY ANALYSES

Unless otherwise stated, all safety analyses will be presented for the FAS.

### 11.1 Extent of exposure

All IMP administration details (including date/time of administration), injection site (left thigh or right thigh), duration of injection (seconds) and comments reported during the administration with the medical device will be listed using the FAS. In addition, a listing of batch and devices numbers used will be created using the FAS.

### 11.2 Adverse events

Adverse events will be recorded from the time of informed consent until study completion. All AEs will be coded (Section 3.7) and categorized by relationship to bimekizumab.

The following definitions will be used in the analysis of AEs:

- A TEAE is defined as any event not present prior to the administration of IMP or any unresolved event already present before administration of IMP that worsens in intensity following exposure to study treatment
- An ADE is defined as any AE related to the use of an investigational medicinal device i.e., where the causality to the device constituent is assessed as ‘related’ by the Investigator
- A serious ADE (SADE) is an ADE that results in any of the consequences defined for a SAE, i.e., where the causality to the device constituent is assessed as ‘related’ by the Investigator and the AE is considered as SAE
- An AE of special interest is any AE that a regulatory authority has mandated be reported on an expedited basis, regardless of the seriousness, expectedness, or relatedness of the AE to the administration of a UCB product/compound. Potential Hy’s Law, defined as  $\geq 3 \times \text{ULN}$  alanine aminotransferase (ALT) or aspartate aminotransferase (AST) with coexisting  $\geq 2 \times \text{ULN}$  total bilirubin in the absence of  $\geq 2 \times \text{ULN}$  alkaline phosphatase (ALP), confirmed by repeat measurement, with no alternative explanation for the biochemical abnormality, must

ALWAYS be reported to UCB as an AE of special interest (i.e., without waiting for any additional etiologic investigations to have been concluded).

By definition, all ADEs and SADEs are also classified as TEAEs.

The number and percentage of participants who experience TEAEs will be summarized by treatment group, SOC, and PT, based on the FAS (unless otherwise stated).

If it is not possible (due to partial dates) to determine whether an AE is treatment emergent or not, it will be assumed to be a TEAE (Section 4.2.4).

An overview of the occurrence and incidence of TEAEs will be provided by treatment group and overall. The overview will present individual occurrences as well as number and percentage of (unique) participants experiencing each of the following:

- TEAEs
- Serious TEAEs
- Discontinuation due to TEAEs
- Drug related TEAEs
- Severe TEAEs
- All Deaths (AEs leading to death)
- Deaths (TEAEs leading to death)
- ADEs
- SADEs.

Summaries of the occurrence and incidence of TEAEs and SAEs will be provided by treatment group and overall. The summary will present individual occurrences as well as number and percentage of (unique) participants, by MedDRA SOC and PT. These summaries will be provided for the following:

- Incidence of TEAEs
- Incidence of serious TEAEs
- Incidence of TEAEs by maximum causal relationship with IMP
- Incidence of TEAEs by maximum intensity
- Incidence of serious TEAEs by maximum causal relationship with IMP
- Incidence of fatal TEAEs by causal relationship with IMP
- Incidence of non-serious TEAEs above threshold of 5% of participants

In summaries including intensity, the following intensity categories will be summarized: 'Mild', 'Moderate', 'Severe'. Participants who experience the same event multiple times will be included in the most severe category for tabulations by maximum intensity. Events with missing intensity will be considered as 'Severe' events for summary purposes but recorded as missing in the listings.

In summaries including causal relationship to IMP, the following relationships will be summarized: 'Not related', 'Related'. Participants who experience the same event multiple times will be included in the most related category for tabulations by maximum relationship. Events with missing causal relationship to IMP will be considered as 'Related' for the tabulations but presented as missing in the listings.

For the summary of non-serious TEAEs above threshold of 5% of participants, only TEAEs which are reported in 5% of participants within a treatment group will be included.

Adverse event summaries will be ordered by alphabetical SOC and decreasing frequency of PT within SOC in the overall column for tables including event counts. For tables including only number and percentage of participants, summaries will be ordered by alphabetical SOC and decreasing incidence of PT within SOC in the overall column.

A listing will be presented by treatment group and participant for all AEs. This will include the onset date/time and outcome date/time of the event (including relative days), the AE duration, pattern of event, intensity, relationship, action taken and outcome. In addition, the listing will flag TEAEs, hospitalization, SAEs, ADEs and AE of special interest. Confirmed and suspected cases of SARS-CoV-2 infection will be recorded as AEs (or SAE, as required).

### 11.3 Clinical laboratory evaluations

Laboratory variables will be grouped according to the laboratory function panel ([Table 11-1](#)) and categorized as normal, high or low, if applicable, based on the reference range supplied by the analytical laboratory.

**Table 11-1: Clinical laboratory measurements**

Category	Panel	Variable
Serology	Serology	HbsAg, HBc-Ab (both IgG and IgM), HCV-Ab, HIV1-Ab, HIV1-Ag, HIV-2 Ab
Hematology	Red blood cell	Hemoglobin a , hematocrit, RBC a
	Platelet	Platelet count a
	White blood cell	WBC count a
	White blood cell differential	Absolute counts: ANC a , basophils, eosinophils, ALC, monocytes Percentages: neutrophils/leukocytes a , eosinophils/leukocytes a , lymphocytes/leukocytes a , monocytes/leukocytes a .
Coagulation/hemostasis	Coagulation	Prothrombin time, aPTT
Clinical chemistry	Electrolytes	Sodium, chloride, potassium, total calcium
	Enzymes	Creatine kinase
	Hormones	FSH

**Table 11–1: Clinical laboratory measurements**

Category	Panel	Variable
	Metabolic	Glucose
	Kidney function	BUN, creatinine
	Proteins	Total protein, albumin a
	Liver function	AST a , ALT a , GGT, ALP, LDH, total bilirubin
	Lipids	Total cholesterol a , LDL cholesterol a , HDL cholesterol, triglycerides
Urinalysis	Dipstick	pH, protein, glucose, ketone, urobilinogen, bilirubin, blood, specific gravity, nitrite, and leukocytes
Other tests	Urine alcohol test/drug screen	Ethanol (measured using a urine alcohol test). Urine drug screen: amphetamines/methamphetamines, barbiturates, benzodiazepines, tetrahydrocannabinol, cocaine, tricyclic antidepressants, phencyclidine, and morphine/opiates
	Pregnancy	Prior to dosing, a serum pregnancy test (hCG) will be performed; post dosing the test may be performed in urine. The FSH test performed in postmenopausal women at the Screening Visit.

ALP=alkaline phosphatase; ALT=alanine aminotransferase; aPTT=activated partial thromboplastin time; AST=aspartate aminotransferase; BUN=blood urea nitrogen; FSH=follicle stimulating hormone; GGT=gamma glutamyl transferase; HBc-Ab=hepatitis B core antibody; HBsAg=hepatitis B surface antigen; hCG=human chorionic gonadotropin; HCV-Ab=hepatitis C virus antibody; HDL=high density lipoprotein; HIV=human immunodeficiency virus; HIV1/2-Ab=HIV1/2 antibody; HIV1-Ag=HIV1 antigen; LDH=lactate dehydrogenase; LDL=low density lipoprotein; RBC=red blood cell; WBC=white blood cell

a Shift table will be presented for this variable

For hematology, coagulation/hemostasis, clinical chemistry and urinalysis laboratory variables the following summaries will be presented by treatment group:

- Observed results and change from Baseline for numeric variables at each post-Baseline time point. These summaries will report the number of participants with non-missing values, mean, SD, median, minimum and maximum.
- Shift tables from Baseline to each post-Baseline time point. These summaries will present a cross-tabulation of Baseline values against post-Baseline values categorized as below normal range, within normal range and above normal range. Each cell will include the corresponding

number and percentage of participants. These summaries will only be presented for selected variables in [Table 11–1](#).

The above-mentioned laboratory variables and change from Baseline for numeric variables will be listed for the FAS by treatment group and time point. Any laboratory measurements that are BLQ or ALQ will be handled as described in [Section 4.2.2](#). Values outside the normal ranges will be flagged and the listings will present reference ranges. Additionally, laboratory results outside reference ranges will be listed by treatment group and time point for the FAS.

Data for the following will only be listed using the ES by treatment group and time point:

- Serology
- Urine alcohol test/drug screen
- Pregnancy tests (serum and urine)
- Follicle stimulating hormone (FSH) (only for postmenopausal women)

### **11.3.1 Potential drug-induced liver injury**

A separate listing will present participants who meet one or more of the following potential drug induced liver injury (PDILI) criteria at any visit:

- Alanine aminotransferase (ALT) or Aspartate aminotransferase (AST)  $\geq 3x$  Upper limit of normal (ULN) and Total bilirubin  $< 2x$  ULN who no exhibit temporally associated symptoms of hepatitis or hypersensitivity
- ALT or AST increase  $\geq 3x$  ULN and Total bilirubin  $\geq 2x$  ULN
- ALT or AST  $\geq 3x$  ULN who exhibit temporally associated symptoms of hepatitis or hypersensitivity

Hepatitis symptoms include fatigue, nausea, vomiting, and right upper quadrant pain or tenderness; hypersensitivity symptoms include eosinophilia ( $> 5\%$ ), rash, and fever (without clear alternative cause).

The listing will display only visits for which at least one of the above criteria was fulfilled for a given participant and will display all results obtained at that visit for the specified parameters.

A summary of participants who met the criteria for PDILI will be presented together with any additional relevant data collected, if applicable.

## **11.4 Vital signs, physical findings, and other observations related to safety**

### **11.4.1 Vital signs**

The following vital signs measurements will be obtained:

- Pulse rate
- Systolic and diastolic blood pressure
- Oral body temperature

Descriptive statistics will be reported for the above vital sign measurements. Measured values and changes from Baseline will be summarized by vital sign variable and time point for each treatment group. These summaries will be presented for the FAS.

By-participant listings of all vital sign measurements and change from Baseline will be presented by treatment group and time point for the FAS.

#### **11.4.2      Electrocardiograms**

Single 12-lead ECG recordings will be taken prior blood sampling and with the study participant resting in the supine position for at least 3 minutes. The following variables will be reported:

- Heart rate
- PR interval
- QRS duration
- QT interval
- QT corrected for heart rate using Fridericia's formula ( $QTcF = QT/RR^{1/3}$ )

The results of all ECG variables will be reported in the by-participant listings for the FAS. The listing will also include the change from Baseline and percentage change from Baseline and will be presented by treatment group and visit/timepoint.

Measured values, changes and percentage changes from Baseline will be summarized for the FAS, for each variable by treatment group and visit/timepoint.

The following cut-points in QTcF (raw data and change from Baseline) will be summarized for the FAS, categorically by treatment group (number and percentage of participants) and visit/timepoint. The denominator for the percentages will be the number of participants with a non-missing measurement for the variable at the specific visit/timepoint.

Raw QTcF data:

- <450msec
- $\geq 450$ msec to <480msec
- $\geq 480$ msec to <500msec
- $\geq 500$ msec

Change from Baseline QTcF:

- <30msec
- $\geq 30$ ms to <60msec
- $\geq 60$ msec

Electrocardiogram findings will be listed separately.

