**Table 1-1: Schedule of activities**

Assessments	Screening	Inhouse Treatment Period			Outpatient Visits			Safety Follow-Up/ Discharge
	Day -28 to Day -2	Day -1	Day 1		Day 1 postdose to Day 3 postdose	Days 4 to 10	Days 13, 16, 19, 22, 25, and 28 ( $\pm 1$ day)	Days 56, 84, 112 ( $\pm 3$ days)
		Admission	Predose	0 h				
Blood samples for ADAbs m			X				X	X
Pregnancy test n	X	X					X	X
Follicle-stimulating hormone test	X							

A=ambulatory; Ab=antibody; ADAb=anti-drug-antibody; AE=adverse event; BP=blood pressure; COVID-19=coronavirus disease 2019; ECG=electrocardiogram; FSH=follicle stimulating hormone; HBsAg=hepatitis B surface antigen; HbC-Ab=hepatitis B core antibody; HCV-Ab=hepatitis C virus antibody; h=hour; HIV=human immunodeficiency virus; HIV1/2-Ab=HIV1/2 antibody; HIV1-Ag=HIV1 antigen; I=inhouse; IgG=immunoglobulin G; IgM=immunoglobulin M; IMP=investigational medicinal product; PK=pharmacokinetic(s); RT-PCR=real-time reverse transcriptase polymerase chain reaction; SARS-CoV-2=severe acute respiratory syndrome coronavirus 2; sc=subcutaneous; SFU=Safety Follow-Up; TB=tuberculosis

Note: At the Investigator's discretion, an Unscheduled Visit may be completed at any time during the study but prior to the SFU Visit, if deemed necessary for the study participant's safety and well-being. The same assessments as performed on the SFU Visit, or alternatively as advised by the Investigator, should be performed if a study participant is attending an Unscheduled Visit during the study.

a Randomization will occur on the evening of Day -1, provided all information for eligibility is known. The study identification card will be given to the study participant following IMP administration.

b Phone calls will be performed 1 day prior to the indicated visit to record signs and symptoms of COVID-19 or any contact with persons having confirmed SARS-CoV-2 infection. In case of signs/symptoms or contact, the visit will be cancelled and reason for cancellation will be appropriately documented.

c Bimekizumab will be administered as a sc injection as detailed in Section 6.

d A full physical examination will be performed at the Screening Visit, Day -1, and SFU Visit. On all other days (Days 2, 3, 9, 25, 56, 84, 112, and 140) a physical examination is planned, it will be performed symptom-driven, ie, in case of an AE.

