## **8.2.5 Clinical safety laboratory assessments**

See Appendix 2 (Section 10.2) for the list of clinical laboratory tests to be performed and the schedule of activities (Section 1.3) for the timing and frequency.

Laboratory data will be electronically captured by ClinBase, a software tool that ensures quality assurance and enables comprehensive capture of all relevant medical information gathered during the study (Section 10.1.6). The Investigator can assess the data in ClinBase and sign off on them electronically.

All laboratory tests with values considered clinically significantly abnormal during participation in the study should be repeated until the values return to normal or baseline or are no longer considered clinically significant by the Investigator or Medical Monitor. If such values do not return to normal/baseline within a period of time judged reasonable by the Investigator, the etiology should be identified and the Sponsor notified.

All protocol-required laboratory assessments, as defined in Appendix 2 (Section 10.2), must be conducted in accordance with the laboratory manual and the schedule of activities (Section 1.3).

If laboratory values from non-protocol specified laboratory assessments performed at the institution's local laboratory require a change in study participant management or are considered clinically significant by the Investigator (eg, SAE or AE), then the results are to be captured in ClinBase.

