## **9.5 Planned safety and immunogenicity analyses**

### **9.5.1 Safety analyses**

All safety parameters will be listed by study participant and treatment group using the FAS.

The incidence of treatment-emergent adverse events (TEAEs) will be determined by treatment group, where applicable. Absolute and relative frequencies for a given TEAE by preferred term as per the Medical Dictionary for Regulatory Activities (MedDRA®), as well as absolute and relative frequencies of individual TEAEs, will be determined within each treatment group and system organ class. Additional tables will summarize TEAEs by maximum event intensity and causal relationship with IMP per treatment group and overall. The actions taken for each TEAE, the time of onset of the TEAE after dosing, and the duration of each AE will be listed. The TEAEs leading to discontinuation and SAEs will also be summarized.

For continuous laboratory variables, values and changes from Baseline will be summarized at each time point. For categorized values according to the reference range, shift tables from Baseline to each postdose time point will be presented for selected variables. Values outside the reference range will be flagged in the data listings. The reference ranges will be reported.

Normal versus abnormal findings for the various ECG parameters and overall ECG will be analyzed as required, focusing on the identification of outliers and of any trends for changes following administration of IMP with respect to QT/QTcF. Descriptive statistics will be presented for ECG value and changes from Baseline over time.

Descriptive statistics will be reported for all vital sign measurements (including systolic and diastolic BP, pulse rate, and tympanic body temperature). Measured values and changes from Baseline will be summarized for all study participants by time point.

Abnormal findings in the physical examination will be presented in listings only.

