#### 4.3 Handling of repeated and unscheduled measurements

All repeated and unscheduled measurements will be presented in the listings. Repeated and unscheduled measurements will not be used for statistical analysis or summary tables, unless the repeated measurement was performed due to unreliable values/technical reasons, or the repeated measurement occurred prior to IMP administration and is defined as the 'Baseline'. The following general rules will apply to all repeated and unscheduled measurements:

- For repeated measurements obtained prior to the IMP administration, the latest reliable value (which may be scheduled or unscheduled) will be used in the calculation of descriptive statistics

- For repeated measurements obtained at any time point after dosing, the first reliable value of any repeated measurements will be used in the calculation of changes from Baseline and for the descriptive statistics.

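### No summary table counts participants with a QTcF outlier or laboratory shift at any time after dosing; the tables are per scheduled time point, and non-technical unscheduled or repeat values stay in listings.

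*SAP*

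**What the plan says.** **QTcF.** SAP 11.4.2 sorts QTcF into bands with limits at 450, 480 and 500 ms, and change from Baseline into bands with limits at 30 and 60 ms. The counts are made "categorically by treatment group (number and percentage of participants) and visit/timepoint", and the denominator is "the number of participants with a non-missing measurement for the variable at the specific visit/timepoint". Protocol 9.5.1 describes the ECG analysis as "focusing on the identification of outliers and of any trends for changes following administration of IMP with respect to QT/QTcF".

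**Laboratory.** SAP 11.3 plans "Shift tables from Baseline to each post-Baseline time point" for selected variables. Protocol 9.5.1 asks for the same layout.

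**Repeat and unscheduled values.** SAP 4.3 states "Repeated and unscheduled measurements will not be used for statistical analysis or summary tables". It makes two exceptions: a repeat done because the value was unreliable or for technical reasons, and a pre-dose repeat that serves as Baseline. When a post-dose measurement is repeated, the first reliable value is used. The same section adds "All repeated and unscheduled measurements will be presented in the listings".

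**Where such values come from.** The note to Protocol Table 1-1 allows an Unscheduled Visit for safety reasons and says "The same assessments as performed on the SFU Visit, or alternatively as advised by the Investigator, should be performed". The SFU assessments include an ECG and safety laboratory tests. Protocol 8.2.5 says that clinically significant laboratory values "should be repeated until the values return to normal or baseline" or until they are no longer considered clinically significant.

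**The concern.** For an outlier endpoint the natural question is how many participants in each arm crossed the limit at least once. The planned tables answer a different one: how many were beyond the limit at each scheduled time point. The rows cannot be added, because the same participant may appear in several of them. The largest row gives only a lower bound on the any-time count.

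The rule in SAP 4.3 adds a second gap. An Unscheduled Visit is held because someone is concerned about a participant, and the protocol plans for ECG and laboratory data from it. A QTcF of 500 ms or more found only at such a visit enters no QTcF category table.

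What is at stake is how readable the safety tables are. A reader comparing the 2 mL and 2x1 mL presentations cannot take from them the number of participants per arm with any QTcF outlier or any shift out of the normal range.

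**Working it through.** The plan states no figure for this point, so there is nothing to reproduce. The check asks how far the by-visit rows fix the any-time count.

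**Inputs from the documents**
- Post-dose ECG time points: 1.5, 5, 11, 24 and 48 h, then Days 9, 25, 56, 84, 112 and 140 (Protocol Table 1-1, footnote f). That gives k = 11.
- Post-dose laboratory time points: Days 2, 9, 25, 56, 84, 112 and the SFU Visit (footnote j). That gives k = 7.
- About 100 participants per arm (SAP 2.4).

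**Assumption.** The documents give no abnormality rate. Take c = 1, 2 or 3 abnormal participants per 100 at every scheduled time point, with the same 100 participants measured each time.

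**Formulas, per 100 participants**
- Fewest ever abnormal (the same people every time): c
- Most ever abnormal (no overlap): c × k
- Expected if time points are independent: 100 × [1 − (1 − c/100)^k]

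For ECG with c = 1, the minimum is 1, the maximum is 1 × 11 = 11, and the independent value is 100 × (1 − 0.99^11) = 10.5.

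| Table | c per time point | Minimum | Maximum | If independent |
|---|---|---|---|---|
| QTcF, k = 11 | 1 | 1 | 11 | 10.5 |
| QTcF, k = 11 | 2 | 2 | 22 | 19.9 |
| QTcF, k = 11 | 3 | 3 | 33 | 28.5 |
| Laboratory, k = 7 | 1 | 1 | 7 | 6.8 |
| Laboratory, k = 7 | 2 | 2 | 14 | 13.2 |
| Laboratory, k = 7 | 3 | 3 | 21 | 19.2 |

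Every line of the planned table would look the same across its whole range. Participants who were abnormal only at an unscheduled visit or on a non-technical repeat would come on top of these counts.

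**Other routes by which an abnormal value is reported**
- *Listings.* All repeat and unscheduled values are listed (SAP 4.3), as are out-of-range laboratory results (SAP 11.3), all ECG results and, separately, ECG findings (SAP 11.4.2).
- *TEAE tables.* Protocol 10.3.1 makes an abnormal laboratory or ECG result an AE if the Investigator considers it clinically significant, and does not limit this to scheduled visits. SAP 11.2 counts unique participants with TEAEs per arm.
- *Liver tests.* SAP 11.3.1 lists participants who meet criteria for potential drug-induced liver injury (PDILI) at any visit and plans a summary of them. It does not say how that summary relates to the exclusion in SAP 4.3.

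What remains without a planned participant-level count is any QTcF outlier, and any laboratory shift outside the PDILI criteria, that was not recorded as an AE.

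**The case against.** The strongest case against is that no data are lost and no protocol commitment is broken. The listings hold every value, and with about 100 participants per arm an any-time count could be made from them. Abnormalities judged clinically significant are counted once per participant in the TEAE tables. Protocol 9.5.1 itself specifies shift tables by time point, and it leaves the ECG normal/abnormal analysis to be done as needed. QTcF bands plus listings do identify outliers. ECG and laboratory data are exploratory endpoints in a single-dose study with the same 320 mg in every arm. Clinically significant ECG changes, with QTcF above 450 ms as an example, exclude a participant at Screening or on Day -1, so counts may well be small.

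Most of this stands. It limits the point to a missing tabulation and rules out several stronger readings that a reader might infer:
- *That any-time abnormalities go unreported.* The listings, TEAE tables and PDILI outputs show otherwise.
- *That an ALT retest crossing 3xULN is excluded from the PDILI summary.* SAP 4.3 describes its rules as general, while SAP 11.3.1 is specific and works on any visit. The text leaves this open.
- *That the tabulated outlier rate is biased low.* This holds only if a per-visit row is read as an any-time rate. For repeats, the first reliable value stays in the table, so the abnormal result that prompted a retest is kept, and later repeats may be closer to normal.
- *That independence gives the upper limit.* It does not: with no overlap the count is 11 per 100, above 10.5.

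The objection does not remove the gap itself. A count made by hand from listings is not a planned output, and the TEAE route depends on Investigator judgement instead of the numeric limits that the SAP sets.

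**Conclusion.** The point holds as a gap in descriptive safety tabulation. No planned table gives the number of participants per arm with any post-Baseline QTcF outlier, or with any laboratory shift outside the PDILI criteria. For QTcF this fits poorly with the protocol's stated focus on outliers. For laboratory shifts the SAP follows the protocol, and the extra row would only improve it.

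On the assumed 1 per 100 at each time point, the any-time count is undetermined between 1 and 11 per 100 for QTcF and between 1 and 7 per 100 for a laboratory variable. The assumed rate is illustrative; nothing in the documents shows that the actual effect would be large. Whether the PDILI summary may use unscheduled values is unstated, and one sentence would settle it. The bioequivalence conclusion is not affected.

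**What to change.** 1. Add one worst post-Baseline value row per arm to the QTcF category table (value and change from Baseline) and to the laboratory shift tables. Use all scheduled, repeat and unscheduled post-dose values. For shift variables, state whether worst means the highest or the lowest value.
2. State in SAP 4.3 that this row is an exception to the exclusion, and that the PDILI summary uses the same any-visit values as the PDILI listing.
3. Keep the scheduled-visit rule for means and changes from Baseline.
4. Footnote that participants with more unscheduled visits have more chances to be counted.

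The cost is one row per table, a short addition to SAP 4.3 and a footnote. No new data are needed. The uneven number of measurements per participant is the one real drawback, and the footnote discloses it.
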